11. ADVERSE EVENTS

The study Investigator and Coordinator will evaluate, characterize and record in the CRF all adverse events (AEs) occurring in all subjects from the initiation of study treatment to study exit (or premature withdrawal). Device or procedure related AEs will be followed until resolution. AEs may be reported spontaneously by the subject or detected by the Investigator or coordinator. AEs should be evaluated for diagnoses not just symptoms (i.e., “angina”, not “chest pain”).

AEs may be either spontaneously reported or elicited during questioning and examination of a subject. All AEs must be completely recorded within the Subject's source documentation. All AEs will be evaluated by the Investigator for relationship to the iovera[°] device and to the treatment.

In addition to verbatim terms, the Sponsor will categorize all AEs using MedDRA preferred terms and system organ classes (SOC). Analysis will report both verbatim and MedDRA terms.

Adverse events¹ (AEs) will be assessed continuously from the initiation of study treatment through study exit. Per ISO14155:2011, an AE is any untoward medical occurrence, unintended disease or injury, or untoward clinical signs in subjects, users or other persons, whether or not related to the investigational medical device. An AE can arise from any use of the device (e.g., off-label use, use in combination with any drug) and from any route of administration.

Timely and complete reporting of all AEs assists the Sponsor in identifying any untoward medical occurrence, thereby allowing:

- 1) protection of the safety of study subjects;
- 2) a greater understanding of the overall safety profile of the device;
- 3) recognition of device-related ill effects;
- 4) appropriate modification of study protocols;
- 5) improvements in study design or procedures; and
- 6) adherence to worldwide regulatory requirements.

11.1 Adverse Device Effect (ADE)

Per ISO14155, an adverse device effect is an adverse event related to the use of an investigational medical device. Adverse events related to the use of iovera[°] include events resulting from insufficient or inadequate instructions for use, deployment, operation or any malfunction of the device. User error or intentional misuse of the device is also defined as an ADE.

ADEs may be either spontaneously reported or elicited during questioning and examination of a subject. All ADEs must be completely recorded within the subject's source documentation and reported to the Sponsor within 48 hours of Investigator becoming aware of the ADE.

11.2 Serious Adverse Event (SAE)/ Serious Adverse Device Effect (SADE)/Anticipated Serious Device Effect (ASADE)/ Unanticipated Serious Adverse Device Effect (USADE)

Per ISO14155, an international clinical trial standard, an SAE is an AE that:

1. Led to a death,
2. Led to a serious deterioration in the health of the subject that
 - a. Resulted in a life-threatening illness or injury,
 - b. Resulted in a permanent impairment of a body structure or a body function,
 - c. Required in-patient hospitalization or prolongation of existing hospitalization,
 - d. Resulted in medical or surgical intervention to prevent permanent impairment to body structure or a body function.

¹ Definition from ISO14155:2011

3. Led to fetal distress, fetal death or a congenital abnormality or birth defect
 An event that is serious must be recorded on the AE worksheet and requires expeditious handling to comply with regulatory requirements.

Events NOT considered to be serious adverse events are:

- Hospitalizations for the treatment, which was elective or pre-planned, of a pre-existing condition that did not worsen, and
- Treatment on an emergency, outpatient basis for an event not fulfilling any of the definitions of “serious” given above and not resulting in hospital admission.

A serious adverse device effect (SADE) is an adverse device effect that has resulted in any of the consequences characteristic of an SAE per the ISO definition.

An SADE which by its nature, incidence, severity or outcome has not been identified in the current version of the risk analysis report is defined by ISO as an unanticipated serious adverse device effect (USADE). Accordingly, an SADE which by its nature, incidence, or severity has been previously been identified in the current version of the risk analysis report is considered an anticipated serious adverse device effect (ASADE).

Any adverse events classified as “serious” by the Investigator or the Sponsor require expeditious handling and reporting to the Sponsor. All SAEs, whether or not the event was related to the study device or anticipated, must be immediately (within 24 hours of becoming aware of the SAE) reported to the sponsor by telephone, email, or confirmed facsimile transmission:

[name], and/or Study Manager
 Myoscience, Inc.
 [REDACTED] (office)
 [REDACTED] (fax)
 [contact]

11.3 AE Severity and Relatedness

Each AE occurring in the study will be characterized by the study Investigator as to severity (Table 3) and relatedness (Table 4).

Table 3. AE Severity Grading System.

Severity Grade	AE Description
Mild	AE is transient and easily tolerated by the subject, even if it causes discomfort
Moderate	AE causes the discomfort and interrupts usual activities
Severe	AE causes considerable interference with usual activities and may be incapacitating or life-threatening

Table 4. AE Relatedness Grading System.*

Grade	Relationship of AE to study device or procedure	Description
5	Definite	An event that follows a reasonable temporal sequence from administration of the study device; that follows a known or expected response pattern to the study device; and that is confirmed by improvement on stopping.

4	Probable	An event that follows a reasonable temporal sequence from administration of the study device; that follows a known or expected response pattern to the study device; and that is unlikely to have been caused by concurrent/underlying illness or other drugs, procedures, or other causes.
3	Possible	An event that follows a reasonable temporal sequence from administration of the study device; that follows a known or expected response pattern to the study device; but may have been caused by concurrent/underlying illness, drugs, procedure, or other causes.
2	Unlikely	An event that does not follow a reasonable temporal sequence from administration of the study device; that does not follow a known or expected response pattern to the study device, or most likely was caused by concurrent/underlying illness, drugs, procedure, or other causes, because of their known effects.
1	Not related	An event almost certainly caused by concurrent/underlying illness, drugs, procedure, or other causes.

*Note that change in medical condition occurring between Screening and the initiation of Study Treatment will be reported as a change in Medical History.

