10.4.4 Safety

Adverse events (AEs) will be coded using the Medical Dictionary for Regulatory Activities (MedDRA). Treatment-emergent AEs (TEAEs) are adverse events with onset after study treatment begins and that are not present at baseline or, if present at baseline, have worsened in severity. For AEs with missing start dates, the AE will be considered treatment-emergent unless there is additional information indicating that the AE started prior to study treatment. Only treatment emergent AEs will be summarized.

The number and percentage of subjects with at least one TEAE, at least one device-related TEAE, at least one serious TEAE, at least one serious adverse device effect, at least one unanticipated serious adverse device effect, at least one anticipated serious adverse device effect, and at least one TEAE leading to study withdrawal will be presented by treatment group. AEs that are definitely, probably, or possibly related to the device, or for which the relationship to the device is missing, will be considered device-related. TEAEs will be summarized at the subject level by MedDRA system organ class (SOC) and preferred term using frequencies and percentages. TEAEs will also be tabulated at the event level by severity and by relationship to the device for each treatment group.

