14.6 Safety Reporting

The Sponsor is responsible for performing ongoing safety evaluation in this study protocol. Sponsor activities regarding safety include:

- classification of all AEs,
- review of all AEs reported in the study,

- confirm site's classification of AEs in terms of severity and relatedness to the study device and/or study procedure,
- review of severity and relatedness with the study Investigator, especially when there is disagreement between the Investigator and the Sponsor,
- review of device deficiencies and malfunctions, including determination and documentation of whether deficiencies/malfunctions could have led to an AE or SAE,
- ensuring the reporting of all SAEs and device deficiencies/malfunctions that could have led to an AE or SAE to the IRB and, if required, regulatory authorities in a timely fashion,
- informing all site Investigators in writing of all SAEs at all sites in a timely fashion and
- updating the risk analysis and assessment of corrective or preventive actions potentially required as a result of new information obtained in the investigation

The Sponsor will evaluate all serious adverse events against US reporting requirements (Medical Device Reporting, 21 CFR 812) and Medical Device Directive (vigilance incident reporting) as per its standard operating procedures. The Sponsor will investigate each SAE to determine whether the event represents an unanticipated serious adverse device effect (USADE, see Section 12.1.2). The Sponsor will report any event to regulatory authorities, Investigators and reviewing IRBs/ECs as necessary. If an investigation shows that a USADE presents an unreasonable risk to subjects, the Sponsor will terminate all investigations or parts of investigations presenting that risk as soon as possible. The Sponsor will only resume a terminated investigation after corrective actions have taken place, site Investigators are informed and IRBs/ECs have been notified and given approval to resume the study.

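### Protocol 11.3 Table 4 requires an already recognised device pattern for every related grade, so, read literally, the investigator cannot grade a new kind of device effect as related

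*Protocol*

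**What the plan says.** Protocol 11.3 has the investigator grade the relatedness of each AE on the five-point scale in Table 4. Besides a reasonable temporal sequence, the top three grades require the following:

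- Grade 5, Definite: "that follows a known or expected response pattern to the study device; and that is confirmed by improvement on stopping".
- Grade 4, Probable: "that follows a known or expected response pattern to the study device; and that is unlikely to have been caused by concurrent/underlying illness", or by other drugs, procedures or causes.
- Grade 3, Possible: "that follows a known or expected response pattern to the study device; but may have been caused by concurrent/underlying illness", or by other such causes.

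Grade 2, Unlikely, lists poor timing, then an event "that does not follow a known or expected response pattern to the study device", then, after a comma and an 'or', an event most likely due to something else. Grade 1 is for events almost certainly due to another cause.

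Protocol 10.4.4 counts as device-related "AEs that are definitely, probably, or possibly related to the device, or for which the relationship to the device is missing". SAP 9.0 applies the same rule to device-, procedure- and opioid-related events.

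Protocol 11.1 defines an ADE simply as an AE related to use of the device. Under 11.2 an SADE is an ADE with a serious outcome, and a USADE is "An SADE which by its nature, incidence, severity or outcome has not been identified in the current version of the risk analysis report". Neither section refers to Table 4.

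**The concern.** Whether the device caused an event and whether that kind of event was foreseen are separate questions. Table 4 merges them by making prior recognition of the pattern a condition of relatedness. The effect falls on events of a new kind, which a post-market safety assessment most needs to pick up.

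Several things turn on an event being considered related: the 48-hour report to the sponsor (Protocol 11.1), follow-up to resolution (Protocol 9.9 and 11), SAP Tables 9.1 to 9.4, and the device- and procedure-related rows of SAP Table 8.1. SAP 9.0 also leaves out the SADE, USADE and ASADE counts listed in Protocol 10.4.4, so its device-attribution summaries rest on the relatedness grade. An absence of new device effects in those summaries could then reflect the wording of the scale and not the data.

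A second, smaller mismatch is that Definite asks for improvement when exposure stops, whereas the device is applied in one session.

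**Working it through.** The plan gives no figure to reproduce, so the check is one of logic.

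**Step 1: criteria side by side (Protocol 11.3, 10.4.4; SAP 9.0).**

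| Grade | Plausible timing | Recognised pattern | Further condition | Counted as related |
|---|---|---|---|---|
| 5 Definite | required | required | improvement on stopping | yes |
| 4 Probable | required | required | other cause unlikely | yes |
| 3 Possible | required | required | other cause may apply | yes |
| 2 Unlikely | absence listed | absence listed | or other cause most likely | no |
| 1 Not related | – | – | other cause almost certain | no |

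**Step 2: all combinations.** Cross timing (yes/no), recognised pattern (yes/no), other cause (unlikely, may apply, most likely, almost certain) and improvement on stopping (yes/no): 2 × 2 × 4 × 2 = 32 combinations, 16 with the pattern and 16 without.

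- Without a recognised pattern, 0 of 16 reach grades 3, 4 or 5.
- With it, 8 of 16 do, namely those with plausible timing. In 4 of these 8 another cause is most likely or almost certain, so grade 2 is also open. Setting those aside leaves 4 of 16; the zero is unaffected.
- Definite is reached in 4 combinations, all with improvement on stopping.

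**Step 3: the event that matters.** Take a new kind of event with plausible timing and no other likely cause. Grades 3 to 5 fail on the pattern, and grade 1 fails because no other cause is almost certain. For grade 2:

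- If its clauses are alternatives, the missing pattern is enough, and the event is Unlikely and not related.
- If its first two clauses apply jointly, as the semicolons do in grades 3 to 5, the event fails on timing; with no other likely cause it fails the third clause too. It then fits no grade.

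On neither reading can the investigator give it a related grade.

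**Step 4: comparison with the definitions.** ADE status in 11.1 needs relatedness only. USADE status in 11.2 can arise because the nature of the effect is not in the risk analysis report. An event can meet both definitions and still have no related grade available in Table 4.

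**Step 5: the stopping criterion.** Grade 5 also requires an event "and that is confirmed by improvement on stopping". Protocol 9.5 describes one complete treatment of the lines, 5 ± 2 days before surgery, and the protocol's Background puts the duration of effect at two to three months. Once the session is over there is no exposure to withdraw. Because grades 3 to 5 are pooled as related, this changes no related count.

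**The case against.** The strongest case on the other side is that the protocol does not rely on the investigator's grade alone.

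- **Serious events.** Protocol 11.2 sends every SAE to the sponsor within 24 hours, related or not. Protocol 14.6 has the sponsor investigate each SAE for USADE status, classify and review all AEs, and discuss relatedness with the investigator where they disagree. Table 4 is assigned to the investigator. This largely stands. Two gaps remain: no relatedness criteria are given for the sponsor other than those in Table 4, and 14.6 points to a Section 12.1.2 for the USADE definition, although Section 12 is Device Tracking and the definition is in 11.2.
- **A generous reading of the scale.** An investigator could take an expected pattern to mean one plausible from the mechanism (cold, nerve block, needle passage). That is possible, but Table 4 does not say so, and grading should not depend on it.
- **Missing counts as related.** True for the tables. But 11.3 requires every AE to be graded, so a blank is not a designed route. It also means that the same event could be tabulated as unrelated (Unlikely) or related (left blank) depending on how grade 2 is read.
- **Nothing disappears.** This stands: SAP Tables 8.1 to 8.3 show all TEAEs whatever their relatedness. What can be lost is attribution to the device and the actions tied to it.

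A reader might infer that a novel harm can never become an SADE or USADE, and so can never reach the rule in 14.6 that "If an investigation shows that a USADE presents an unreasonable risk to subjects, the Sponsor will terminate all investigations" or parts of them presenting that risk. The documents do not support this, because the sponsor's determination covers each SAE whatever its grade. A reader might also infer that no event can be Definite. That is too absolute: treatment consists of successive insertions in awake subjects, and an event during the session could improve when it ends.

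**Conclusion.** The defect holds in a limited form. On the literal text, every related grade requires a recognised pattern (0 of 16 combinations without one qualify), which conflicts with Protocol 11.1 and 11.2. The practical exposure is mainly novel non-serious events. They get no individual USADE investigation, and they can miss the 48-hour report, follow-up to resolution and the device- and procedure-related tables. Serious events are largely covered by the sponsor's own investigation. The stopping criterion is a poor fit with little consequence.

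The primary endpoint and its analysis are not affected. This should be corrected, but it does not undermine the trial.

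No misgrading rate can be given. The chance of seeing some assumed new event among about 60 iovera subjects would measure its occurrence, not its misclassification. The conclusion assumes that Table 4 is applied as worded and that no other grading guidance overrides it; the protocol and SAP contain none.

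**What to change.** Amend Protocol 11.3 Table 4:

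1. In grades 3 to 5, let a recognised pattern support relatedness without being required, for example: known response pattern, or otherwise plausibly caused by the device or procedure.
2. In grade 2, remove an unknown pattern as a sufficient reason for Unlikely, and make clear whether the remaining clauses are alternatives or joint conditions.
3. In grade 5, replace the stopping criterion with one that a one-time treatment can meet, such as direct evidence at the treatment site with no plausible alternative cause.
4. State that anticipatedness is judged separately, against the risk analysis report as in 11.2. Reconcile Table 4 with 11.1, 11.2 and 14.6, including the criteria the sponsor uses for relatedness and the cross-reference to the USADE definition.

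The rule pooling grades 3 to 5 as related can stay. The cost is an amendment, with the IRB approval that Protocol 14.4 requires, and a short CRF guidance note; no visits, subjects or data items are added. The downside is that slightly more events may be graded Possible, so the device-related count may look a little less favourable.

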12. DEVICE TRACKING

The Sponsor will send the investigational devices to study sites. The Investigator must house study devices in a secure location. The Investigator must carefully and completely track receipt, use and disposition of all investigational devices. The Sponsor will track sending and receiving of devices. The Sponsor will monitor site device accountability periodically.

If a Sponsor representative or designee is present at the time of use, he/she may directly take possession of used device(s). All devices will be returned to the Sponsor after the study is complete.

13. DEVICE DEFICIENCIES AND MALFUNCTIONS

Throughout the study, the Investigator and study staff will report and document all device deficiencies and malfunctions related to the identity, quality, durability, reliability, safety or performance of the device. This includes reporting of device deficiencies/malfunctions that did not lead to an AE but could have if: 1) suitable action had not been taken, 2) intervention had not been made, or 3) circumstances had been less fortunate. If possible, the Investigator should return devices suspected of deficiency or malfunction to the Sponsor for analysis.

14. ETHICAL AND REGULATORY CONSIDERATIONS

14.1 Compliance with Good Clinical Research Practice

This study will be conducted in compliance with the principles of the Declaration of Helsinki, with the current Good Clinical Practice (GCP) guidelines and with other applicable regulations. The Investigator and all study staff will conduct the study in compliance with this protocol. Voluntary informed consent will be given by every subject prior to the initiation of any study-related procedures. The rights, safety and well-being of the study subjects are the most important considerations and prevail over the interests of science and society. All personnel involved in the conduct of this study must be qualified by education, training and experience to perform their assigned responsibilities.

14.2 Institutional Review Board (IRB) and Informed Consent

Before study initiation, the Investigator must have written and dated approval from the IRB for the protocol, consent form, subject recruitment materials/process (e.g., advertisements), and any other written information to be provided to subjects. The Investigator should also

provide the IRB with a copy of the product labeling, information to be provided to subjects and any updates. The Investigator will submit documentation of the IRB approval to the Sponsor. Copies of all correspondence with the IRB regarding this study must be sent to the Sponsor.

The IRB-approved consent form must include all elements required by FDA, state, and local regulations, and may include appropriate additional elements.

The Investigator/designee will explain the study to each potential subject and the subject must indicate voluntary consent by signing and dating the approved informed consent form. The Investigator must provide the subject with a copy of the consent form in a language the subject understands. The Investigator will maintain documentation that informed consent was obtained prior to the initiation of any study-specific procedures.

Withdrawal of IRB approval of the Investigator's part in the investigation must be reported to the Sponsor within 5 working days.

14.3 Protocol Compliance

The Investigator will comply to the extent possible with the IRB-approved protocol. All deviations from the protocol must be documented. The Investigator will notify the Sponsor immediately if a deviation from the protocol was required to protect patient safety.

14.4 Protocol Revisions

Revisions to the study protocol can be made only by the study Sponsor. A revised protocol can be put into place only after governing IRB approval. All administrative letters must be submitted to the IRB for their information.

New or altered consent forms required by the IRB due to a protocol change must be signed by all subjects currently enrolled in the study and must be used for any subsequent subject enrollment.

14.5 Study Monitoring

Representatives of the Sponsor will visit all study sites intermittently to review study records and to directly compare them with source documents (including, but not limited to patient and hospital records), to discuss the study conduct with the Investigator and study staff and to verify that the Investigator, study staff and facilities remain acceptable for the conduct of the study.

Representatives of government regulatory authorities may also evaluate the study records, source documents, Investigator, study staff and facilities.

The Investigator should immediately notify the Sponsor of any audits of this study by any regulatory agency, and must promptly provide copies of any audit reports.

